1 STUDY SYNOPSIS

0	
Sponsor /	
Principal	PD [name]
Investigator	
	A neuromuscular warm-up program to prevent injuries in basketball – a cluster-randomized
Title of Study	controlled trial
Short title	A neuromuscular warm-up program to prevent injuries in basketball
Version and date	
of protocol	02 (28.09.2022)
••• p. ••• ••	The study will be registered at the «Koordinationsstelle Forschung am Menschen» (kofam:
Study	https://www.kofam.ch/). The trial has been registered at the «ISRCTN registry»
Registration	(https://www.isrctn.com/).
Study Category	A
	Basketball players have an increased risk of lower body injuries (especially knee and ankle).
	These injuries typically occur during single-leg jump landings. Because severe injuries carry
Background	
	the risk of long-term health consequences and prolonged interruptions in athletic activities
	and/or an active lifestyle, preventive measures are essential.
	Intervention-related foreseeable risks and/or discomforts (physical) that could reasonably be
	anticipated are lower than those encountered in regular training and competition. Participants
Diek her stit	from the intervention group will be instructed to focus on proper technique, movement
Risk-benefit	awareness, and body positioning during warm-up, thereby minimizing the injury risk.
assessment	Due to data safety reasons and to comply with the data privacy protection, all data will be
	stored separately from any names or other direct identification of participants. In addition, the
	records will be stored electronically on password-protected computers in Excel files at all times.
	Only research personnel will have access to participant personal data.
a	The aim of this study is to assess the effectiveness of a specifically designed five-phase
Study aim	neuromuscular warm-up protocol (which incorporates basketball-specific drills) in reducing the
	incidence rate of injuries.
	Primary endpoint:
	Incidence rate of lower extremity injuries
	Secondary endpoints:
	Incidence rate of
Endpoints	overall injuries
•	severe injuries (lay-off time of more than 28 days)
	joint-ligament injuries
	muscle injuries
	ankle injuries
	knee injuries
	upper extremity injuries
Study design	A two-arm, single-centre cluster-randomised controlled trial (level of evidence 1)
	R (Project for Statistical Computing) and Jamovi will be used for statististical analyses. The
Statistical	injury incidence rate will be calculated as follows: [(number of events during a specified
considerations	period)/(total athlete-exposures at risk during a specified period)] x 1000. We will calculate
	incidence rate ratios together with 95% confidence intervals to assess the risk difference
	between the intervention and the control group.
	Inclusion criteria
	1) ≥16 years of age; 2) >2 years' experience in organized basketball training and competition
Inclusion and	immediately prior to participation in the study; 3) officially registered teams. Exclusion criteria
exclusion criteria	1) regular training takes place less than twice per week; 2) teams already apply an injury
	prevention program or a structured warm-up focusing on neuromuscular control.
	No restrictions will be set according to sex.
	An a priori analysis using G*Power software (version 3.1.7; Heinrich Heine University
Sample size	Düsseldorf, Düsseldorf, Germany) for proportions (using a 2-tailed alpha value of 0.05, and
	power of 0.80) recommended a sample size of 124 (62 per group), based on previous research

	reporting a total of 32 injuries (17.5% in intervention group compared to 41.4% in control group)	
	during the 9-month season.	
Intervention	A specifically designed five-phase (20 min) neuromuscular warm-up protocol will be integrated within the regular training routines. At the beginning of the season, each coach will obtain an exercise manual including a detailed description of the setup, all the exercises (including different difficulty levels), and additional background information concerning posture corrections and proprioception. Intervention components are designed to include running (running straight ahead, running high-knees, running glute-kick, hip out, hip in, leg crossovers), plyometrics, balance, strength (walking lunge, double leg jump – double leg landing, single leg jump to double leg jump, double leg jump – highest point catch – double leg landing, single leg jump – highest point catch – single leg landing, double leg jump – two handed pass, wall sit, ball release core rotations, plank, side plank) and agility drills (mirror forwards and backwards, mirror side shuffle), replicating a basketball-specific workload as recommended from the literature.	
Control	Teams from the control group will be instructed to perform their usual warm-up routine.	
Study conduct	 Eligible participants will be randomly assigned to a control or intervention group. A specially designed five-phase (20-minute) neuromuscular warm-up protocol will be incorporated into regular training routines in the intervention group. Teams in the control group will be instructed to perform their usual warm-up program. During the first weeks of the season, study assistants will visit the intervention group teams and provide instruction to the coaches on the proper use of the intervention program. In addition, two unannounced visits (by study assistants) will be made to each team in the intervention group during the study period. For each team, the contact person (preferably, but not necessarily, the coach) will be instructed to report injuries that occurred during a scheduled game or practice session that resulted in the player being unable to complete the current game or practice session and/or fully participate in the next game or practice session. The characteristics of the injury, including location, type, and mechanism, as well as the time the player was unable to participate in the sport, will be reported by the coach or other contact person (therapist, physician) on a weekly injury report form via email to the researcher (who is blind to group assignment). If an athlete is injured we will contact her/him to find out the more specific circumstances of the injury. If an injury requires medical treatment, we will ask the 	
Study duration and time plan	athlete to get the exact diagnosis from the treating physician.The study begins in September 2021 and will end in June 2022. In September athletes and coaches will be instructed on the coduct of the training programme and on the proper reporting of exposure times and injuries. Data acquisition starts mid-September.First-Participant-In: 15.09.2021 Last-Participant-Out: 30.06.2022	
Research team	PD [name] Head Section Exercise and Movement Science Department of Sport, Exercise and Health, Medical Faculty, University of Basel Address: [name] T [contact] Email: [contact] [name] Department of Sport, Exercise and Health, Medical Faculty, University of Basel Address: [name] [contact]	
Study center	Department of Sport, Exercise and Health, Medical Faculty, University of Basel	
Data security	The principal investigator/sponsor confirms and defends the principle of the right to privacy of the participants. This means that both the applicable data protection laws will be complied with and the anonymity of the participants will be guaranteed when the data are presented at scientific meetings or published in scientific journals. Medical information about individual subjects obtained in the course of this study is considered confidential. In this regard, disclosure to third parties is prohibited. Confidentiality is further assured by the use of subject identification numbers corresponding to treatment data in computer files. Participant data will be handled with uttermost discretion and will be only accessible to authorised personnel who require the data to fulfil their duties within the scope of the study.	

	On the CRFs and other study specific documents, participants will be only identified by a unique participant number. The principal investigator will retain a confidential master list linking the participants' unique study numbers with participant names. The records will be stored electronically on password-protected computers in Dropbox folder to ensure safety back-ups
	or protect from unauthorised or accidental disclosure, alteration, deletion, copying and theft. In
	addition, all files will be secured in locked cabinets. The high participation in sports activities has resulted in sports being the primary cause of
Ethical considerations	injury, with probably the highest injury rates in competitive athletes. Many injuries most often leads to decline in performance, loss of playing time, a high financial burden for the athlete's employer as well as the healthcare system, and an increased risk of re-injury and chronicity. In this regard, prevention of basketball injuries would be beneficial to basketball players, teams, the Swiss Basketball Federation, health insurance companies, and society. To date, the equivocal findings have been reported regarding the effect of neuromuscular training on the incidence rate of injury in basketball players. Although neuromuscular training has the potential to enhance stability, muscular strength, motor control and reduce the risk of injury, injury prevention program should be designed to better replicate basketball-specific movement patterns. The risk of injury will be minimized by using research participants that have experience with neuromuscular training, placing the focus on proper technique, movement awareness, body positioning and basketball-specific activity demands. All data will be handled with uttermost discretion and will be only accessible to participant or authorised personnel who require the data to fulfil their duties within the scope of the study. Participant may choose not to participate or you may discontinue your participation at any time without penalty.
	This study will be conducted in accordance with the current version of the Declaration of
GCP declaration	Helsinki, the ICH-GCP, the HRA as well as relevant local legal and regulatory requirements.

2 BACKGROUND AND RATIONALE

Basketball is a sport that places high demands on the lower extremities, which can lead to an increased risk of injury. The lower limbs (63.7%) are the most affected injury region in basketball players (1). Two basketball-related injuries that traditionally receive the most attention are ankle sprains and knee injury [particularly of the anterior cruciate ligament (ACL)], accounting for 15% and 23% of all basketball injuries in males and females (2). Sports-related injuries are a substantial contributor to the health care costs in Switzerland, estimated at over 931 million Swiss francs per year, of which the highest costs resulted from ACL reconstruction, particularly in team sports (3). Epidemiological data reveal a worrying increase in the incidence of ACL reconstructions in young athletes (4). An ACL injury has serious consequences for the injured athlete, in terms of not only treatment costs and time lost from sport, but also a greatly increased risk of early osteoarthritis. While ankle sprains are relatively less severe than ACL injury in terms of time lost from sport, prevention efforts are important, considering the increased risk of recurrent sprain, concomitant injury to the talus and peroneal musculature, and the development of chronic ankle instability (5, 6) with subsequent osteoarthritis that can follow initial ankle sprains (7).

Given the high incidence rates and long-term consequences associated with ankle and ACL injury, extensive research (8-17) has been performed to design and implement injury prevention programs in basketball players; however, with equivocal findings. To date, eight studies (10-17) have examined the effects of injury prevention programs on the incidence rate of lower extremity injuries [six studies for ankle injury (10-14, 16) and knee injury (10-12, 15-17)] in basketball players. While some prevention programs have been found to be effective in reducing lower extremity injuries [ankle(10, 13) and knee(12)], the majority of the existing studies show non-significant differences on decreasing the risk of ankle injury (4 out of 6 studies = 67%)(11, 12, 14, 16) and knee injury (5 out of 6 studies = 83%) (10, 11, 15-17). In addition, two meta-analyses by Taylor et al. (6) and Michaelidis et al. (18) failed to show any effect of prevention programs on ACL knee injury rate in basketball players. While Taylor et al. (6) confirmed the effectiveness of neuromuscular training and external support (e.g. ankle bracing) on reducing the risk of ankle sprains, the precise influence of the training procedure remains unclear since a pooled meta-analytic approach was applied.

Despite growing interest in quantifying the effects of injury prevention programs in basketball players, there are still many practical aspects that should be addressed. To date, injury prevention programs have been uniformly implemented across basketball and soccer athletes. Since "FIFA 11+" has been shown to be effective in preventing injuries in soccer players (19), two studies (11, 16) have implemented this program in male and female basketball players, showing no reduction in ankle and knee injury rates. The implementation of an injury prevention program, which was developed for a specific sport like soccer, with a majority of the plyometric exercises emphasizing double-leg sagittal plane movements, may not be appropriate for basketball players, considering differences in activity demands between basketball and soccer (20). While both sports are multi-directional, basketball requires more abrupt stops, cutting, movements in the frontal plane (e.g. lateral shuffling), and single-leg jump landings than soccer on a different surface (21, 22). These basketball-specific tasks impose elements of dynamic lower extremity valgus, placing basketball players in potentially higher-risk positions for ACL injuries, which typically occur during single-leg jump landings (about 70%) (20). Therefore, an injury prevention program should be developed to better replicate the multidirectional, high-intensity activity demands experienced during game-play. Focus on basketball-specific movement patterns and the correct technique might contribute to the development of more adequate interventions and to the selection of effective strategies in reducing and minimizing the risk of injury in basketball players. Considering the role of the feedback in effective teaching motor skill and neuromuscular control, foreseeable risks and/or discomforts (physical) that could reasonably be anticipated during specifically designed warm-up are lower than those encountered in regular training and competition (A category according to ClinO, Art. 61).

3 STUDY OBJECTIVES AND DESIGN

3.1 Hypothesis and primary objective

Hypothesis:

A specifically designed training program can be effective in reducing the incidence rate of injury in basketball players.

Objective:

The aim of this study is to assess the effectiveness of a specifically designed five-phase neuromuscular warm-up protocol (which incorporates basketball-specific drills) in reducing the incidence rate of injuries.

3.2 Primary and secondary endpoints

Primary endpoint: Incidence rate of lower extremity injuries

Secondary endpoints:

Incidence rate of ...

- ... overall injuries
- ... severe injuries (lay-off time of more than 28 days)
- ... joint-ligament injuries
- ... muscle injuries
- ... ankle injuries
- ... knee injuries
- ... upper extremity injuries

3.3 Study design

A two-arm, cluster-randomised controlled trial (level of evidence 1) will be adopted in this study, and conducted as a single-centre study in Switzerland. To reduce potential confounding, the teams will be matched by sex and playing level. All teams will be randomly allocated to a control

or intervention group in a 1:1 ratio. The researcher who conduct the randomization will not be involved in the intervention, and recruitment will be completed before randomization. Computer-generated cluster randomization will be conducted using Research Randomizer software (https://www.randomizer.org/).

3.4 Study intervention

A specifically designed five-phase (20 min) neuromuscular warm-up protocol will be integrated within the regular training routines. At the beginning of the season, each coach will obtain an exercise manual including a detailed description of the setup, all the exercises (including different difficulty levels), and additional background information concerning posture corrections and proprioception. Intervention components are designed to include **running** (running straight ahead, running high-knees, running glute-kick, hip out, hip in, leg crossovers), **plyometrics, balance, strength** (walking lunge, double leg jump – double leg landing, single leg jump to double leg jump, double leg jump – highest point catch – double leg landing, single leg jump – highest point catch – single leg landing, double leg jump – two handed pass, wall sit, ball release core rotations, plank, side plank) and **agility drills** (mirror forwards and backwards, mirror side shuffle), replicating a basketball-specific workload as recommended from the literature. Teams from the control group will be instructed to perform their usual warm-up routine, including light aerobic exercises, basketball and team drills, and dynamic stretching.

Upon regular study completion, participants from both groups (intervention and control) may choose their preferable warm-up routine (specifically designed or usual).

4 STUDY POPULATION AND STUDY PROCEDURES

4.1 Inclusion and exclusion criteria, justification of study population

Officially registered basketball teams in Switzerland will be invited to participate in the study. The following inclusion criteria will be applied: 1) \geq 16 years of age; 2) >2 years' experience in organized basketball training and competition immediately prior to participation in the study; 3) officially registered teams. Teams will be excluded if 4) regular training takes place less than twice per week; 5) teams already apply an injury prevention program or a structured warm-up focusing on neuromuscular control (apart from light aerobic exercise, basketball and teams drills, and dynamic stretching). No restrictions will be set according to sex. Initial screening questions will qualify or disqualify respondents from taking the study.

4.2 Recruitment, screening and informed consent procedure

Officially registered basketball teams competing in the first, second and third division of the Swiss Basketball League will be invited (via e-mail) to participate in this study in August till mid-September 2021. Information meetings will be also conducted to inform coaches about the aims and procedures of the study and, for intervention group only, to give detailed instructions and practical application on the warm-up programme. The institutional/organizational permission will be obtained to ensure access to all members of the basketball team before recruiting participants. Potential participants maintain their right to refuse or withdraw from participation. To protect the privacy interests and minimize the possibility of undue influence (e.g. peers), decision to take part in the research will be made in the absence of other team members."

The investigators will explain to each participant the nature of the study, its purpose, the procedures involved, the expected duration, the potential risks and benefits and any discomfort it may entail. Each participant will be informed that the participation in the study is voluntary and that he or she may withdraw from the study at any time and that withdrawal of consent will not affect his or her subsequent medical assistance and treatment. The participant will be informed

that his or her medical records may be examined by authorised individuals other than their treating physician. Two weeks will be given to the potential participant to consider fully the likely implications of the research before making a decision.

The formal consent from all participants with parental consent for those <18 years of age (using the approved consent form) will be obtained before the participant is submitted to any study procedure. The consent form will be signed and dated by the investigator or his designee at the same time as the participant sign. A copy of the signed informed consent will be given to the study participant. The consent form will be retained as part of the study records. No compensation will be provided to the study participants.

4.3 Study procedures

The observation period will comprise one basketball season from September/October 2021 to May/June 2022. To ensure recruitment of participants, an information sheet containing exclusion/inclusion criteria will be distributed to all basketball teams in August 2021. After signing informed consent forms, eligible participants will be assigned to a control or intervention group in a 1:1 ratio. Teams who meet an acceptance rate of 70% from the roster list will be included in the study.

Data on medical history, age, height, body mass, training characteristics, injury history, basketball experience, and competition level will be collected at baseline. Injury characteristics, including location, type, mechanism, as well as time loss from sport will be reported by the coach or other contact person (therapist, medical doctor) on a weekly injury report form to the researcher (blinded to group allocation) via email (23). For each team, the contact person (preferably, but not necessarily the coach) will be instructed to report injuries that occurred during a scheduled match or training session, causing the player to be unable to complete the current match or training session and/or to fully take part in the next match or training session. If an injury requires medical treatment, basketball player will be instructed to obtain the exact diagnosis from the treating physician. Injury rates will be reported as number of injuries per 1000 athlete exposures. Exposure is defined as one athlete participating in one practice or match. Coaches will register individual playing time (min) and absences (due to an injury) for each training session and match during the season.

4.4 Withdrawal and discontinuation

Participants may be withdrawn from the study due to a safety concern or if judged non-compliant with trial procedures. The participant must be withdrawn from treatment if one of the following applies:

- > Participant decide to stop taking part in this study at any time
- Pregnancy during study duration
- Major violation of the study protocol

In case of withdrawal, identifiable data of participants will be kept confidential. All data will be stored separately from any names or other direct identification of participants.

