5.2 Handling of missing data and drop-outs

All randomized subjects will be included in the group which they were originally assigned, regardless of adherence to treatment protocol (eg, dropout/withdrawal or protocol deviations). Thus, all data will be analyzed on an intention-to-treat basis. The missing data will replaced with the last observation carried forward.

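### Section 4.4 lets players be withdrawn from the study for non-compliance without providing for continued injury and exposure recording, which undermines the intention-to-treat analysis in Section 5.2

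*Protocol*

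**What the plan says.** Section 4.4 of the protocol contains two withdrawal rules. The first is discretionary and concerns the study: "Participants may be withdrawn from the study due to a safety concern or if judged non-compliant with trial procedures". The second is mandatory and concerns treatment: "The participant must be withdrawn from treatment if one of the following applies". The list under the second rule includes "Major violation of the study protocol". On what happens to data after withdrawal, the section speaks only of confidentiality and separate storage of names: "In case of withdrawal, identifiable data of participants will be kept confidential".

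Section 5.2 sets the analysis principle: "All randomized subjects will be included in the group which they were originally assigned, regardless of adherence to treatment protocol (eg, dropout/withdrawal or protocol deviations". It adds one rule for gaps: "The missing data will replaced with the last observation carried forward".

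The primary endpoint (Section 3.2) is the incidence rate of lower extremity injuries. Section 5.1 calculates rates as events divided by athlete-exposures. On the comparator, Section 3.4 says: "Teams from the control group will be instructed to perform their usual warm-up routine, including light aerobic exercises, basketball and team drills, and dynamic stretching".

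**The concern.** An intention-to-treat comparison needs outcomes for everyone randomised over the planned follow-up, and not only a rule about the arm in which each player is counted. Section 4.4 makes non-adherence a ground for leaving the study. Section 5.2 says non-adherence must not affect who is analysed. If leaving the study ends recording, the rate in an arm is estimated with the later time of its non-adherent players missing.

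This matters if those players have a different injury rate from the rest, either because they were at different risk to begin with or because they were not receiving the benefit of the warm-up. The rate ratio would then move towards an effect in adherent players while still being labelled intention-to-treat. This cannot be left to a statistical analysis plan. It is a conduct rule fixed in the protocol, and no analysis recovers data that were never collected.

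**Working it through.** **Passages side by side**

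1. Section 5.2 keeps a withdrawn player in the assigned arm. With a rate endpoint this preserves the injuries and exposures accrued up to withdrawal, and nothing after it.
2. Carrying the last observation forward does not fill the gap. If cumulative totals are frozen, the result is the same as dropping the later time. If the last weekly report is repeated, exposures and injuries are invented. Neither gives what happened.
3. Section 4.4 does not say what withdrawal from the study, or withdrawal from treatment, means for follow-up. The terms are not kept apart: a decision to stop taking part in the study is listed under withdrawal from treatment. Pregnancy is also on that list, while Section 6.5 describes it as withdrawal from the study. These passages must be reconciled.

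**Illustration A: no true effect**

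The protocol gives no figure on this point to reproduce, so every input here is assumed. Let f be the share of intervention players withdrawn, r their injury rate relative to the other players, and t = 1/3 the part of the season followed before withdrawal. Both arms have the same mix of players, exposure is even over time, the control arm is followed in full, and its rate is scaled to 1. The rate in the other players is a = 1/[(1−f) + f·r]. With later time dropped,

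IRR = [(1−f)·a + f·r·a·t] / [(1−f) + f·t].

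- f = 0.2, r = 1.5: a = 1/1.1 = 0.909; IRR = (0.727 + 0.091)/0.867 = 0.944
- f = 0.2, r = 2: a = 1/1.2 = 0.833; IRR = (0.667 + 0.111)/0.867 = 0.897
- f = 0.3, r = 1.5: a = 1/1.15 = 0.870; IRR = (0.609 + 0.130)/0.8 = 0.924
- f = 0.3, r = 2: a = 1/1.3 = 0.769; IRR = (0.538 + 0.154)/0.8 = 0.865
- f = 0.05, r = 1.5: a = 1/1.025 = 0.976; IRR = (0.927 + 0.024)/0.967 = 0.984
- any f, r = 1: a = 1, numerator equals denominator, IRR = 1

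With r below 1 the shift goes the other way.

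**Illustration B: a true effect**

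Assume a rate ratio of 0.50 in adherent players and 1.0 in non-adherent players, a share w withdrawn, and t = 0.25 to 0.50. Full follow-up gives (1−w)·0.5 + w. Cut follow-up gives [(1−w)·0.5 + w·t]/[(1−w) + w·t].

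- w = 0.05: 0.525 in full; 0.506 to 0.513 when cut
- w = 0.20: 0.600 in full; 0.45/0.85 = 0.529 to 0.50/0.90 = 0.556 when cut
- w = 0.30: 0.650 in full; 0.548 to 0.588 when cut

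No difference in underlying risk is needed here. Removing unprotected time from the intervention arm is enough.

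**The case against.** The best defence is that the protocol nowhere says recording stops. Injuries are reported by a team contact, coaches register every session (Section 4.3), and coaches are contacted weekly about all activity and new injuries (Section 8.2). A withdrawn player who stays on the team could still appear in those reports. The rule is also permissive, so it may rarely be used. This stands as far as it goes: the fair criticism is that continued recording is not provided for, and not that it is known to cease.

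A reader might infer several stronger things that the documents do not support.

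- *That the intention-to-treat analysis is defeated or cannot be built.* Section 5.2 expressly keeps withdrawals and deviations in the assigned arm, so earlier data count.
- *That the loss falls mainly on the intervention arm.* This is plausible, since controls keep their usual routine and the synopsis places the unannounced visits in intervention teams. But Section 4.4 refers to trial procedures in general, reporting duties apply to both arms, and Section 9 describes visits to each team.
- *That people who know the allocation decide.* Section 4.4 names no assessor.
- *That a major violation ends follow-up.* That item is listed under withdrawal from treatment. Read literally, it is compatible with Section 5.2.

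The shifts are also modest against random error. Treating the planning percentages as event counts gives 62 × 0.175 = 10.9 and 62 × 0.414 = 25.7 events. The standard error of the log rate ratio is then about √(1/10.9 + 1/25.7) = 0.36, ignoring clustering. The four Illustration A shifts at 20% and 30% withdrawn with r of 1.5 to 2 are about 0.06 to 0.15 on that scale. That limits the weight of the point. It does not remove it, because a confidence interval does not reflect bias of this kind.

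**Conclusion.** The concern holds in a limited form. Section 4.4 permits withdrawal from the study for non-compliance and is silent on recording afterwards. That undermines, without defeating, the analysis promised in Section 5.2, and the stated missing-data rule does not repair it. The two kinds of withdrawal also need defining in terms of follow-up.

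The size cannot be determined from the protocol, which gives neither a non-compliance rate nor the risk of non-compliant players. Illustration A ranges from no bias (equal risk) through 0.98 (5% withdrawn, 1.5 times the risk) to 0.87 (30% withdrawn, twice the risk), against a true value of 1. Illustration B shows an intention-to-treat ratio of 0.60 appearing as 0.53 to 0.56 with 20% withdrawn. Both assume that withdrawals occur only in the intervention arm and that recording stops when they do. A larger loss in that arm is a reasonable expectation from the design, but the documents do not state it.

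**What to change.** Leave the reasons for stopping the warm-up as they are. In Section 4.4, remove non-compliance as a reason to end study follow-up and say what each kind of withdrawal means for data collection. Suggested sense: stopping or not performing the warm-up, or a protocol violation, does not end the recording of injuries and exposures; recording continues through the team reports to the end of the season unless the player withdraws consent to data collection. Reconcile Sections 4.4, 5.2 and 6.5 on the same terms.

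In the trial report, give withdrawals by arm, reason and date.

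The cost is a few sentences, since session registration and weekly contact already exist. The synopsis dates protocol version 02 as 28.09.2022 and the last participant out as 30.06.2022. If the season is over, new wording cannot recover unrecorded data, so the report should also say whether team records exist for withdrawn players after they left and, where consent allows, use them.
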